"Compared to the patient's condition (i) Visit 2 (prior to medication) versus (ii) Visit 4 (end of medication) OR (i) Visit 4 (end of medication) versus (ii) Visit 6 (end of washout) OR (i) Early Termination Visit versus (ii) previous visit, this patient's condition is: 1=very much improved since the initiation of treatment; 2=much improved; 3=minimally improved; 4=no change from baseline (the initiation of treatment); 5=minimally worse; 6= much worse; 7=very much worse since the initiation of treatment."

The Clinical Global Impression of Change (CGI-C) - caregiver asks the caregiver one question:

"Compared to the patient's condition (i) Visit 2 (prior to medication) versus (ii) Visit 4 (end of medication) OR (i) Visit 4 (end of medication) versus (ii) Visit 6 (end of washout) OR (i) Early Termination Visit versus (ii) previous visit, how much has he/she changed: 1=very much improved since the initiation of treatment; 2=much improved; 3=minimally improved; 4=no change from baseline (the initiation of treatment); 5=minimally worse; 6=much worse; 7=very much worse since the initiation of treatment."

The Clinical Global Impression of Change (CGI-C) - patient asks the patient ($if\ able$) one question:

"Compared to how you were (i) Visit 2 (prior to medication) versus (ii) Visit 4 (end of medication) OR (i) Visit 4 (end of medication) versus (ii) Visit 6 (end of washout) OR (i) Early Termination Visit versus (ii) previous visit, how much have you changed: 1=very much improved since the initiation of treatment; 2=much improved; 3=minimally improved; 4=no change from baseline (the initiation of treatment); 5=minimally worse; 6=much worse; 7=very much worse since the initiation of treatment."

The CGI-C – clinician/caregiver/patient will be assessed at the time points designated on the schedule of events (Appendix 3A for "naïve" patients and Appendix 3B for "non-naïve" patients).

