7.1.2 Baseline Visit (Visit 2)

Visit 2 (Baseline 2): Day 14 (+7 days) after Visit 1 (Baseline 1). The final day/ second assessment of the baseline period. The start of the treatment period.

- Reconfirm patient eligibility, including confirmation that prohibited medications have not been used since **Visit 1**
- Documentation of frequency of therapy (hours per week)
- Documentation of concomitant medication
- · Vital signs
- Spinocerebellar Ataxia Functional Index (SCAFI) + Video-Recording for Clinical Impression of Change in Severity (CI-CS) Anchor Tests (9HPT-D and 8MWT)
- Scale for Assessment and Rating of Ataxia (SARA)
- Quality of Life EQ-5D-5L for patients aged ≥18 years, EQ-5D-Y for patients aged
 18 years
- Modified Disability Rating Scale (mDRS)
- Clinical Global Impression of Severity (CGI-S) by physician
- Clinical Global Impression of Severity (CGI-S) by caregiver
- Clinical Global Impression of Severity (CGI-S) by patient if able
- Urinalysis (done at central lab)
- Urine by dipstick: pregnancy test for women of childbearing potential (done at site before first dose of study drug is taken)
- Urine test for N-Acetyl-D-Leucine (test done at PK lab)
- Blood draw for safety laboratory tests (done at central lab)
- Blood draw for sparse PK (done at PK lab)
- Documentation of adverse events
- Dispensing of trial drug + intake of study drug at site

7.1.3 *Treatment 1 (Visit 3)*

Visit 3 (Treatment 1) Day 28 (+7 days) of treatment period: First assessment of treatment period with N-Acetyl-L-Leucine.

- Return of trial drug and compliance check (if feasible)
- Documentation of frequency of therapy (hours per week)
- Documentation of concomitant medication
- Vital signs
- Spinocerebellar Ataxia Functional Index (SCAFI) + Video-Recording of Clinical Impression of Change in Severity (CI-CS) Anchor Tests (9HPT-D and 8MWT)
- Scale for Assessment and Rating of Ataxia (SARA)
- Quality of Life EQ-5D-5L for patients aged ≥18 years, EQ-5D-Y for patients aged <18 years
- Modified Disability Rating Scale (mDRS)
- Clinical Global Impression of Severity (CGI-S) by physician
- Clinical Global Impression of Severity (CGI-S) by caregiver
- Clinical Global Impression of Severity (CGI-S) by patient if able
- 12-lead ECG
- Urinalysis (done at central lab)
- Blood draw for safety laboratory tests (done at central lab)

- Blood draw for sparse PK (done at PK lab)
- Documentation of adverse events
- Dispensing of additional study drug if needed

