7.1.6 Washout Visit 2 (Visit 6)

Visit 6 (Washout 2): Day 42 (+7 days) of washout period: the final day/second assessment of washout period.

- Documentation of frequency of therapy (hours per week)
- Documentation of concomitant medication
- Vital signs
- Spinocerebellar Ataxia Functional Index (SCAFI) + Video-Recording of Clinical Impression of Change in Severity (CI-CS) Anchor Tests (9HPT-D and 8MWT)
- Scale for Assessment and Rating of Ataxia (SARA)
- Quality of Life EQ-5D-5L for patients aged ≥18 years, EQ-5D-Y for patients aged <18 years
- Modified Disability Rating Scale (mDRS)
- Clinical Global Impression of Severity (CGI-S) by physician
- Clinical Global Impression of Severity (CGI-S) by caregiver
- Clinical Global Impression of Severity (CGI-S) by patient if able
- Clinical Global Impression of Change (CGI-C) by physician based on Visit 4 to Visit 6
- Clinical Global Impression of Change (CGI-C) by caregiver based on Visit 4 to Visit 6
- Clinical Global Impression of Change (CGI-C) by patient if able based on Visit 4 to Visit 6
- Medication History: If the patient was classified as "naïve", confirm if they have used N-Acetyl-Leucine (L, DL, D) at any time prior to Visit 1
- Urinalysis (done at central lab)
- Urine by dipstick: pregnancy test for women of childbearing potential (done at site)
- Urine test for N-Acetyl-D-Leucine (done at PK lab)
- Blood draw for laboratory safety tests (done at central lab)
- Blood draw for sparse PK (done at PK lab)
- Documentation of adverse events
- Investigator determines continued treatment with IB1001 in patient's best interest (if applicable)
- Informed consent/informed consent form (ICF) signature and patient information for Extension Phase (if applicable)
- Check of inclusion/exclusion criteria for Extension Phase (if applicable)

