6.1 Updated Efficacy Parameters

6.1.1 Measurement of Global Impression

The clinical global impression of severity (CGI-S) and change (CGI-C) will continue to be measured, with the questions for the physicians, caregivers, and patients modified to accommodate the Extension Phase visits.

Physician, Caregivers, and Patients (if able) will be asked to assess the CGI-S at each visit (Visit 7, Visit 8, Visit 9, Visit 10, Visit 11, Visit 12 and at the Extension Phase Early Termination visit, if applicable). The question is identical to that described in the Parent Study Section 6.1.5.

Physician, Caregivers, and Patients (if able) will be asked to assess the CGI-C at Visit 8, Visit 9, Visit 10, Visit 11, Visit 12, and the Extension Phase Early Termination Visit (if applicable).

"Compared to the patient's condition at:

(i) Visit 7 (extension phase baseline) versus (ii) Visit 8 (interim extension phase treatment visit) OR versus Visit 9 (end of extension phase treatment);

OR

(i) Visit 9 (end of extension phase treatment) versus (ii) Visit 10 (end of extension phase washout);

ΟR

(i) Visit 10 (end of extension phase washout) versus (ii) Visit 11 (interim extension phase treatment visit) OR versus Visit 12 (end of extension phase treatment period II);

(i) Early Termination Visit versus (ii) the previous visit,

this patient's condition is: 1=very much improved since the initiation of treatment; 2=much improved; 3=minimally improved; 4=no change from baseline (the initiation of treatment); 5=minimally worse; 6= much worse; 7=very much worse."

CONFIDENTIAL Version 7.0, 10 Oct 2022 Page 136 of 161

The Clinical Global Impression of Change (CGI-C) - caregiver asks the caregiver one question:

"Compared to the patient's condition at:

(i) Visit 7 (extension phase baseline) versus (ii) Visit 8 (interim extension phase treatment visit) OR versus Visit 9 (end of extension phase treatment);

 ΩR

(i) Visit 9 (end of extension phase treatment) versus (ii) Visit 10 (end of extension phase washout);

OR

(i) Visit 10 (end of extension phase washout) versus (ii) Visit 11 (interim extension phase treatment visit) OR versus Visit 12 (end of extension phase treatment period II);

OR

(i) Early Termination Visit versus (ii) the previous visit,

how much has he/she changed: 1=very much improved; 2=much improved; 3=minimally improved; 4=no change; 5=minimally worse; 6=much worse; 7=very much worse."

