The mDRS composite score and individual components (ambulation, language, manipulation, swallowing, seizures, and ocular movement) will be summarized using descriptive statistics at each visit. As graphical display, a stacked bar chart of the 6 mDRS subscores at each visit will be created. Spaghetti plots of individual patient mDRS composite scores versus time will be made as well as a mean or median display versus time, depending upon the distribution, and corresponding two-sided 90% CI at each visit.

Furthermore, changes in the mDRS composite score between Visit 2 and Visit 4 as well as between Visit 4 and Visit 6 will be descriptively presented in a summary table.

Measurement of Global Impression

The three CGI-S scores (scored by treating physician, caregiver, and patient) will be summarized using descriptive statistics and frequency tables for each visit.

Bar charts will be presented for the three CGI-S scores, spaghetti plots of individual CGI-S scores versus time will be made as well as a mean or median display versus time, depending upon the distribution, and corresponding two-sided 90% CI at each visit.

Descriptive statistics and frequency tables will also be used to summarize the three CGI-C scores (treating physician, caregiver and patient) between Visit 2 and Visit 4, and between Visit 4 and Visit 6, and corresponding bar charts will be created.

The CGI-C scores for Visit 4 versus Visit 2, and for Visit 6 versus Visit 4 will be evaluated using descriptive statistics. Similarly, the CGI-C from Visit 2 to Visit 4 minus the CGI-C from Visit 4 to Visit 6 will be presented descriptively. In addition, the CGI-C measures for treating physician will be analyzed similar to the primary endpoint: the CGI-C from Visit 2 to Visit 4 minus the CGI-C from Visit 4 to Visit 6 will be compared to a difference of zero using a one-sample t-test or Wilcoxon signed-rank test.

Note that CGI-C is referred to as CGI-I in the eCRF.

It is important to realize that the CGI-S and CGI-C scores per visit for each patient as provided by the caregiver may be based on varying caregivers and hence additional variation is introduced. No correction for this variation can be done and a footnote will be added to the table to describe this situation.

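### At Visit 6 the CGI-C question asks for change since Visit 4, but options 1, 4 and 7 refer to the start of treatment at Visit 2

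*Protocol*

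**What the plan says.** Protocol 6.1.5 gives one CGI-C question each for physician, caregiver and patient. The question offers alternative comparisons, and the one for the end of washout is "i) Visit 4 (end of medication) versus (ii) Visit 6 (end of washout". At Early Termination the comparison is with the previous visit.

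One list of options follows all the comparisons. Its upper part reads "1=very much improved since the initiation of treatment; 2=much improved; 3=minimally improved; 4=no change from baseline (the initiation of treatment", and the physician form ends "4=no change from baseline (the initiation of treatment); 5=minimally worse; 6= much worse; 7=very much worse since the initiation of treatment". Options 1, 4 and 7 therefore name the start of treatment; options 2, 3, 5 and 6 name no reference. The caregiver and patient forms carry the same three anchors. Protocol 7.1.2 places the start of treatment at Visit 2: "The final day/ second assessment of the baseline period. The start of the treatment period".

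The schedule and the analysis use Visit 4 as the reference:

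- Protocol 7.1.6 lists "Clinical Global Impression of Change (CGI-C) by physician based on Visit 4 to Visit 6".
- SAP 5.6.3 states that, for the physician, "the CGI-C from Visit 2 to Visit 4 minus the CGI-C from Visit 4 to Visit 6 will be compared to a difference of zero", by a one-sample t-test or Wilcoxon signed-rank test. Caregiver and patient CGI-C are descriptive.
- SAP 4.1.3 describes the scale labels without any reference visit.
- SAP 11.3 lists the difference test as Table 14.2.57, and tests of each period's physician score as Table 14.2.58.

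In the Extension Phase (Protocol Appendix 6, 6.1.1) the physician form still reads "this patient's condition is: 1=very much improved since the initiation of treatment" and keeps the anchor in option 4. Its option 7 is clean. The Extension caregiver and patient forms carry no anchor at all.

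**The concern.** The question and three of its answers point to different times. For the Visit 2 to Visit 4 rating this is harmless, because both references are Visit 2. At Visit 6 they separate, and they do so for the pattern the design is meant to pick up: gain on drug, loss after withdrawal. Such a patient is worse by the question and unchanged by option 4.

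No section says which reference prevails. Two physicians seeing the same course could give different scores, and the Visit 4 to Visit 6 score would then mix two quantities. The physician version matters most, because it is the only CGI-C that is formally tested and the test uses that score directly.

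The Early Termination comparison has the same conflict whenever the previous visit was later than Visit 2, although that rating is not one of the two scores in the tested difference. In the Extension the conflict is clearest for Visit 9 versus Visit 10.

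**Working it through.** **Plan's own figure.** The documents give no effect size, SD or power for CGI-C, so there is none to reproduce. The only stated power is for the primary CI-CS difference, used below as an illustration.

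**Inputs.** The scale runs from 1 (best) to 7 (worst), with 4 as no change (Protocol 6.1.5). The tested quantity is the Visit 2 to 4 score minus the Visit 4 to 6 score, compared with zero (SAP 5.6.3).

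**Algebra.** Let a be the true change from Visit 2 to Visit 4 and b the true change from Visit 4 to Visit 6, in scale steps with plus meaning better. The Visit 4 rating is 4 - a under either reading.

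- Visit 6 by the question: rating 4 - b. Difference = (4 - a) - (4 - b) = b - a.
- Visit 6 by the option text: rating 4 - (a + b). Difference = (4 - a) - (4 - a - b) = b.

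The readings differ by a, the whole on-treatment change. On the raw scale a negative difference means benefit.

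| Course | Visit 4 rating | Difference by question | Difference by options |
|---|---|---|---|
| Minimally improved, full reversal (a=1, b=-1) | 3 | 3 - 5 = -2 | 3 - 4 = -1 |
| Much improved, full reversal (a=2, b=-2) | 2 | 2 - 6 = -4 | 2 - 4 = -2 |
| Minimally improved, gain kept (a=1, b=0) | 3 | 3 - 4 = -1 | 3 - 3 = 0 |
| Minimally worse, stays worse (a=-1, b=0) | 5 | 5 - 4 = +1 | 5 - 5 = 0 |

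The first two rows need only option 4 to be read literally. The last two need the rater to carry the anchor over to options 3 or 5, which do not print it. The last row shows that the effect is not simply conservative, since worsening on drug would also be hidden.

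**Illustration of power, on borrowed inputs.** Protocol 8.10 gives mean 0.45, SD 1.02, n = 30 and 76% power at one-sided 5%. The noncentral t distribution with 29 degrees of freedom and noncentrality (0.45/1.02) × √30 gives 76.3%, so the stated figure reproduces.

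Now apply these inputs to CGI-C. Assume half the effect arises in each period, and a and b have equal variance and correlation r. From 1.02² = 2s²(1 - r), the SD of b is s = 1.02/√(2(1 - r)). If every physician follows the options, the mean is 0.45/2 = 0.225:

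| r | SD of b | Power |
|---|---|---|
| -0.5 | 0.589 | 66% |
| 0 | 0.721 | 51% |
| 0.5 | 1.02 | 32% |

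If half do, the mean is (0.45 + 0.225)/2 = 0.3375 and power is 55% to 69% over the same range of r. If all do and the whole effect is on-treatment gain, the mean is 0 and power is 5%.

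**The case against.** The strongest reply is that the intended reference is plain. The question, the visit procedures and the SAP all say Visit 4 to Visit 6, and the SAP labels are neutral, so the anchors look like leftover wording. Four of the seven options carry no anchor, and the correct answers for a patient who loses benefit in washout, 5 or 6, are among them. The eCRF page is not in the documents. The SAP works from a separate annotated CRF and notes that the eCRF calls this scale CGI-I, so the form raters saw may differ from the protocol text.

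All of that stands, and it limits the claim. It does not remove the contradiction in the protocol, because option 4 is the answer a literal reader would choose for a patient back at the Visit 2 state.

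A reader might infer that the physician result is distorted as a matter of fact, or that every option has the wrong reference. The documents support neither: rater behaviour is unknown and only options 1, 4 and 7 are affected. A reader might also infer that the Visit 2 to Visit 4 score should replace the difference as the tested result. That would take the withdrawal component out of an unblinded rating in a single-arm study and depart from the synopsis, which analyses physician CGI-C as the primary endpoint. Table 14.2.58 already provides the Visit 2 to Visit 4 test, so the replacement is not needed.

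**Conclusion.** The mismatch is certain on the current text; its effect on the data is conditional. In the limiting case where all physicians follow the option text, each patient's difference loses the full on-treatment change, leaving the washout change alone. For full reversal that halves the difference. The actual loss depends on the share of raters who read it that way, which the documents do not give. The step arithmetic treats ordinal categories as evenly spaced, and the power figures borrow CI-CS inputs with assumed correlations, so they show a possible range and do not estimate CGI-C power.

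The consequence is bounded. SAP 5.1 treats everything other than the primary endpoint as exploratory. The CI-CS is unaffected, because its blinded raters compare two videos. Extension CGI-C is descriptive only (SAP 6.6.3 and 6.6.4). This is a wording fault worth correcting in a tested secondary endpoint and no threat to the trial's main conclusion.

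**What to change.** In Protocol 6.1.5, on all three Parent Study forms, remove the reference to the start of treatment from options 1 and 7 and everything after 'no change' from option 4. Do the same for options 1 and 4 of the physician form in Appendix 6, 6.1.1. Every option then takes its reference from the question, at Visit 6, Early Termination and Visit 10 alike, as the Extension caregiver and patient forms already do. Check the eCRF page and correct it if it prints the same text.

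For Visit 6 ratings already collected on the present wording, keep the planned difference test. Add a footnote on the wording to Tables 14.2.57 and 14.2.58, and read the difference beside the Visit 2 to Visit 4 physician test in Table 14.2.58, where question and options agree. On the 1 to 7 coding that single-period score should be tested against 4, which is no change. The Visit 4 to Visit 6 test in the same table shares the wording problem.

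The cost is one questionnaire page and a table footnote. The drawback is that washout ratings made on the two wordings are not strictly comparable.

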6.1.6 NPC Clinical Severity Scale (NPC-CSS)

The NPC clinical severity scale (NPC-CSS) [Yanjanin et al, 2010] was developed and validated in a cross-sectional study of current NPC patients and a longitudinal chart review of an historical cohort. The scale quantifies the major symptoms of NPC and characterizes the disease progression of NPC. The NPC-CSS measures clinical signs and symptoms in 9 major

CONFIDENTIAL Version 7.0, 10 Oct 2022

(ambulation, cognition, eye movement, fine motor, hearing, memory, seizures, speech, swallowing) and 8 minor (auditory brainstem response, behavior, gelastic cataplexy, hyperreflexia, incontinence, narcolepsy, psychiatric, respiratory problems) domains. A higher NPC-CSS score indicates a more severe clinical impairment and higher disease burden. An increase in the NPC-CSS score indicates a clinical worsening, while a decrease NPC-CSS score indicates a clinical improvement. A 0-point change in the NPC-CSS score represents a stabilization of disease progression, which is also a significant clinical improvement for rapidly progressive, neurogenerative diseases like NPC.

NPC-CSS is a widely accepted clinical outcome measure for NPC trials that investigate long-term treatment effect. Several clinical trials in patients with NPC have change in the NPC-CSS as primary endpoint, including a Phase IIb/III clinical trial of 2-hydroxypropyl- β -cyclodextrin (VTS-270; ClinicalTrials.gov ID: NCT02534844), a Phase II/III clinical trial of arimoclomol (NCT02612129), and an open-label Phase I/II clinical trial of lithium carbonate (NCT03201627). The ongoing Phase II/III trial of arimoclomol over 12 months has a modified version of the NPC-CSS as a primary endpoint, which includes 5 NPC-CSS domains: ambulation, speech, swallowing, cognition, and fine motor skills (EudraCT No. 2015-004438-93). These domains were identified by Cortina-Borja et al. (2018) as the most important manifestations of the disease for patients with NPC.

A recent consensus paper on clinical management guidelines for Niemann-Pick disease type C recommended that, bearing in mind the resources available to most physicians in practice, a modified version of the NPC-CSS that is widely used in clinical practice, and more user-friendly, should be administered. This modified version excludes the hearing and auditory brainstem response domains [Geberhiwot et al, 2018]. Accordingly, all major and minor domains of the NPC-CSS [Yanjanin et al, 2010] will be assessed in this study, with the exception of the hearing and auditory brainstem response domains. The change in the full NPC-CSS score, apart from hearing domains (i.e. hearing and auditory brainstem response), will be calculated.

In addition, the 5-domain version of the NPC-CSS (limited to the 5 major domains ambulation, cognition, fine motor, speech, and swallowing) which has been demonstrated to be a reliable surrogate for the complete NPC-CSS scale will be assessed [Cortina-Borja et al, 2018; Mengel et al, 2020].

The NPC-CSS / 5-Domain NPC-CSS is included as an exploratory endpoint in the Parent Study, as it may not sensitive enough to detect short-term changes in disease severity.

6.1.7 Remote Assessments

Due to COVID-19, safety and efficacy parameters may be collected remotely in lieu of inperson assessments (as feasible).

6.2 Safety Parameters

The Investigator is responsible for monitoring the safety of patients who have been enrolled in this study and for accurately documenting and reporting information as described in this section.

In addition, the investigator will monitor the degree of stress to patients and the risk threshold throughout the trial.

CONFIDENTIAL Version 7.0, 10 Oct 2022 Page 47 of 161

6.2.1 Adverse Events

Patients will be instructed to report to the Investigator any AE that they experience. Investigators will ask about the occurrence of AEs at each visit. Investigators are required to document all AEs occurring during the clinical study, commencing with the signing of the informed consent form (ICF) through the End of Study Visit (scheduled at 42 days post last IB1001 dose). Adverse event recording will continue for patients who discontinue study treatment but remain on-study, until their ET Visit has been completed.

Adverse events will be recorded on designated eCRF pages. Each AE is to be characterized (i.e., verbatim term) and information provided regarding its seriousness, start and stop dates, intensity, outcome, and causal relationship with the study drug.

An AE is any undesirable physical, psychological or behavioral effect experienced by a patient during participation in an investigational study, in conjunction with the use of the drug or biologic, whether or not product-related. This includes any untoward signs or symptoms experienced by the patient from the time of signing of the informed consent until completion of the study.

Adverse events may include, but are not limited to:

- Subjective or objective symptoms spontaneously offered by the patient and/or observed by the Investigator or medical staff
- · Findings at physical examinations
- Laboratory abnormalities of clinical significance

Disease signs, symptoms, and/or laboratory abnormalities already existing prior to the use of the investigational product are not considered AEs after treatment unless they reoccur after the patient has recovered from the preexisting condition or, in the opinion of the Investigator, they represent a clinically significant exacerbation in intensity or frequency. Clinical significance is defined as any variation in signs, symptoms, or testing that has medical relevance and may result in an alteration in medical care. The Investigator will continue to monitor the patient until the assessment returns to Baseline or until the Investigator determines that follow-up is no longer medically necessary.

An AE does not include:

- Medical or surgical procedures (e.g., surgery, endoscopy, tooth extraction, transfusion); the
 condition that leads to the procedure is an adverse event; Planned surgical measures
 permitted by the clinical study protocol and the condition(s) leading to these measures are
 not adverse events, if the condition(s) was (were) known before the start of study treatment.
 In the latter case, the condition should be reported as part of the subject's medical history.
- Pre-existing diseases or conditions present or detected prior to the start of study drug administration that do not worsen;
- Situations where an untoward medical event has not occurred (e.g., hospitalization for elective surgery, social and/or convenience admissions).

It is important that Investigators record accurate AE terms on eCRFs. Wherever possible, a specific disease or syndrome rather than individual associated signs and symptoms will be identified by the Investigator and recorded on the eCRF. However, if an observed or reported

sign or symptom is not considered a component of a specific disease or syndrome by the Investigator, or is atypical, it should be recorded as a separate AE on the eCRF.

